Half of participants will be randomized to the control group. For the length of the intervention period and for two weeks of follow-up, subjects will receive a weekly telephone call, lasting approximately 10-15 minutes, to assess health and social activities.

C. Blinding

1. Assessor Blinding

Staff conducting cognitive assessments will be blinded to subject group assignment. Subjects will be instructed and reminded to maintain blinding throughout the study.

The Social Isolation Assessment requires asking about conversation frequency. To preserve blinding to subject group assignment, conversation frequency should **not** be assessed at the Month 6 time

point by the blinded assessor. The conversation frequency portion of the assessment should be done by study staff who are not blinded to subject group assignment.

2. Intervention Staff Blinding

Staff administering the video chat intervention will be blinded to subject cognitive status (normal vs. MCI).

3. Investigator Blinding

Investigators will not be blinded to subject allocation, however when making ongoing eligibility or subject termination decisions, investigators should attempt to discuss the situation and make ongoing participation determinations without awareness of subject group assignment to the degree possible (i.e. by not referencing the subject's ID number or identity while assessing the situation with staff).

V. Study Population

A. Number of Subjects

The targeted study population remains as described in the main I-CONNECT study protocol. We anticipate enrolling approximately 40 subjects across study sites under this Remote Protocol.

B. Inclusion and Exclusion Criteria

Inclusion Criteria:

- 1) Age 75 or older
- 2) Consent to participate in the study
- 3) Socially isolated, defined by **at least one** of the following:
 - i. Score ≤ 12 on the 6-item Lubben Social Network Scale (LSNS-6)
 - ii. Engages in conversations lasting 30 minutes or longer no more than twice per week, per subject self-report
 - iii. Answers "Often" to at least one question on the Hughes et al. Three-Item Loneliness Scale
- 4) Adequate vision to use study technology and complete all neuropsychological tests throughout the study, defined by the following:
 - i. Able to see well enough to read a newspaper, wearing glasses if needed but not using a magnifying glass
- 5) Adequate hearing to use study technology and complete all neuropsychological tests throughout the study, defined as:

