The Social Isolation Assessment requires asking about conversation frequency. To preserve blinding to subject group assignment, conversation frequency should not be assessed at the Month 6 time point by the blinded assessor. The conversation frequency portion of the assessment should be done by study staff who are not blinded to subject group assignment.

3. The Neuroticism-Extraversion-Openness Five-Factor Inventory (NEO-FFI) Baseline, Month 6

¹ Hughes, M. E., Waite, L. J., Hawkey, L. C., & Cacioppo, J. T. (2004). A Short Scale for Measuring Loneliness in Large Surveys: Results From Two Population-Based Studies. *Research on aging, 26*(6), 655–672. doi:10.1177/0164027504268574

The NEO-FFI is a self-report personality inventory. The questionnaire will be provided for subjects to complete independently at the Baseline and Month 6 time points. If the subject does not successfully complete the questionnaire on his or her own, the questionnaire will be completed with staff assistance.

4. Genotyping *Baseline*

A single saliva sample will be self-collected to measure APOE4, a genetic risk factor for Alzheimer's disease. Participants will be permitted to opt out of sample collection and genetic testing. Participants will not be given the results of their genetic test. If it is not possible to obtain a saliva sample at the designated time point, collection may be re-attempted at a future time point. If a saliva sample is determined inadequate, an additional sample may be requested at a future time point.

B. Administrative Procedures

1. Pre-Visit Stability Screening *Screening, Month 6*

At the beginning of every assessment call, study staff will complete the Pre-Visit Stability Screening. Subjects will be asked about their health, routines, and substance use.

Based on the participant's responses, study staff will assess whether reasonably reliable data can be collected, and determine if the call be rescheduled and/or if data collected should be flagged during analysis for any reason. This screening facilitates consistency of testing conditions across all assessment calls.

If time point assessments are split into multiple visits (e.g. multiple visits for screening, or multiple visits for Month 6), this screening should be administered at each visit.

2. Subject Contacts *Screening*

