Chats will be scheduled at consistent times throughout the subject's participation in the study. Chats may be rescheduled as needed. If a given day's chat cannot be successfully rescheduled, the chat will be considered missed. Chats missed due to planned holiday office closures will not be considered protocol deviations. If a technical issue renders a video chat impossible for a given day, the chat may be conducted via telephone.

After every chat, study staff will complete a questionnaire assessing qualitative aspects of the chat such as perceived subject engagement level. Adverse events incidentally noted during intervention delivery will be handled as described in the Data & Safety Monitoring Plan (DSMP).

2. Positive and Negative Affect Schedule (PANAS) *Weekly During Intervention Period & Dose Tapering*

The PANAS is a self-report mood questionnaire which will be administered to subjects in the intervention group only. It will be administered at both the beginning and the end of the subject's first video chat session each week.

3. I-CONNECT Weekly Questionnaire *Weekly During Intervention Period & Dose Tapering*

Health and social activities will be monitored with a brief survey, the I-CONNECT Weekly Questionnaire, administered verbally during a weekly phone call lasting approximately 10-15

minutes. Subjects in both the experimental and control groups will complete these calls. Calls will be audio recorded.

Staff will call the subject at a prescheduled time to conduct the questionnaire. If the subject does not answer, staff may reattempt contact with the subject. If the subject cannot be reached after reasonable attempts, the weekly call will be considered missed.

Adverse events will be noted in the course of conducting the weekly health questionnaire. Adverse events will be documented, assessed and reported per DSMP and OHSU IRB requirements.

4. Medication Adherence *Intervention Period Weeks 1-4, Follow-Up Period Weeks 25-27*

At the OHSU study site, daily vitamin-taking adherence will be tracked as a real-world measure of cognitive function. Subjects will be provided with electronic pillboxes and low-dose (250 mg) vitamin C tablets. Please refer to the Risks and Benefits section for additional information.

A pillbox will be provided for four weeks of data collection to begin at Week 1 Day 1, and three weeks of data collection to begin at Week 25. An adequate supply of tablets will be supplied with the pillbox.

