At the conclusion of the intervention period, the video chat technology (and vitamin C pillbox, if applicable) and any accompanying study equipment will be returned, either via prepaid mail or contactless pickup from the home. Subjects will self-uninstall equipment for return to the study.

J. Follow-Up

1. Dose Tapering Weeks 25-26

Subjects in the experimental group will receive a decreased dose of the video chat intervention in Weeks 25 and 26. They will chat twice per week. They will also continue to receive the PANAS during the first video chat session of the week.

This tapered dose is intended to reduce the risk of loneliness associated with an abrupt end to chats, and to create consistent testing conditions between this remote protocol and the main I-CONNECT protocol, facilitating data analysis.

Subjects in both the control and experimental groups will continue to receive weekly health calls during Weeks 25 and 26 as well, mirroring the conditions of the main I-CONNECT protocol.

2. Follow-Up Call Week 28

Subjects will receive a follow-up call approximately one month after the conclusion of the intervention period (refer to Schedule of Events). If participants become depressed, as evidenced by their scores on the Geriatric Depression Scale (GDS), staff will provide information about mental health resources and may refer the subject to the subject's primary care physician. Subjects will be encouraged to utilize the post-study social engagement resources.

K. Subject Discontinuation

1. Early Termination

If at any point during the study it is determined that the subject no longer fulfills study eligibility criteria, the investigator will assess whether the subject should be withdrawn and may choose to terminate the subject's participation. To the degree possible, the investigators should avoid referencing or considering study group assignment when assessing potential discontinuation. If a subject is terminated for any reason, study staff will arrange for the uninstallation of study equipment from the subject home, and subjects will be provided with post-study resources for

social engagement.

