Participants may or may not directly benefit from participating in the study. However, their contribution to research may help further the development of user-friendly, in-home sustainable approaches to improving neurophysiological, cognitive, and emotional health into old age. Ultimately, this research may contribute to the larger goal of delaying the onset of Alzheimer's disease.

XI. Schedule of Events

A. Procedure Timing Guidelines:

- All visits from Screening through the Technology Installation should be completed

approximately **within a ten-week window**.

- **Screening Time Point:** Screening procedures should all be completed approximately **within a two-week window**. Events may be split across multiple days/visits at site discretion to accommodate practical concerns such as participant fatigue, scheduling, or distance from the study center.
- **Clinician Diagnosis:** **Within approximately one week** of completing final Screening procedures.
- **Baseline Visit:** **Within approximately one week** following the clinician diagnosis.
- **24-Week Intervention Period:** starts after the final Baseline Period visit. Week 1 of the intervention period will always begin on a Monday.

Baseline Period visits include the Baseline assessment visit, the technology installation visit (as applicable), and the Baseline MRI (as applicable). For all subjects, **Week 1 will start no more than two Mondays after the last Baseline Period procedure.**

- **Month 6 Time Point:** Procedures should all be completed **within a two-week window**, during intervention period **weeks 25-26**. Events may be split across multiple days/home visits at site discretion.

B. Table: Schedule of Events

Time Point Name	Screening Period		Baseline Period		Intervention Period	Follow-Up Period			
	Telephone Pre-Screening	Screening	Baseline	Tech Install		Dose Tapering	Month 6	Tech Uninstall	Telephone Follow-Up
Approximate Time Required	30 min.	3 hours	30 min.	1-2 hrs.	6-54 hrs.	.5-2 hrs.	2 hrs.	30 min.	30 min.
Scheduling Timeframe		10-Week Window			Weeks 1-24	Weeks 25-26	Week 25-26	Week 27-28	Week 28
Collect Informed Consent		X							
Pre-Visit Stability Screening ^r		X	X				X		
Collect PCP/Contact Information ^a		X							
Demographics (Form A1)		X							
Social Isolation Assessment	X	X					X ^t		X
GDS (Form B6) ^p		X					X		X
T-Cog Neuropsychological Battery ^q		X					X		
CDR (Form B4)		X					X		
Subject Health History (Form A5)		X							
Medication Assessment		X					X		

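### At OHSU, study-supplied vitamin C runs at least a week past the last listed physical-health enquiry; the existing Week 28 call could cover that week

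*Combined protocol and SAP*

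**What the plan says.** **Adverse-event route.** Section VI.H.3 (I-CONNECT Weekly Questionnaire) states: "Adverse events will be noted in the course of conducting the weekly health questionnaire". Section VI.H.1 adds that events coming up by chance during chats are handled under the Data and Safety Monitoring Plan (DSMP).

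**When those contacts end.** For controls, section IV.B says: "For the length of the intervention period and for two weeks of follow-up, subjects will receive a weekly telephone call". Section VI.J.1 says both arms "will continue to receive weekly health calls during Weeks 25 and 26 as well". In the same two weeks the intervention arm has its taper chats: "They will chat twice per week".

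**Stability screening.** Section VI.B.1 includes questions on health: "At the beginning of every assessment call, study staff will complete the Pre-Visit Stability Screening". Its stated use is that "study staff will assess whether reasonably reliable data can be collected". The section heading names Screening and Month 6; the Schedule of Events also marks Baseline, but not Telephone Follow-Up. Section XI.A places the Month 6 procedures in Weeks 25-26 and adds: "Events may be split across multiple days/home visits at site discretion".

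**Vitamin C.** Section VI.H.4 and notes m and u of the Schedule of Events give OHSU subjects one 250 mg tablet a day in Weeks 1-4 and again in Weeks 25-27.

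**Last call.** Section VI.J.2: "Subjects will receive a follow-up call approximately one month after the conclusion of the intervention period". The schedule puts it in Week 28, allows 30 minutes, and marks the Social Isolation Assessment, the GDS and post-study resources.

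**The concern.** The study supplies a tablet that section X.A.4 says may carry some risk of gastrointestinal effects, especially in subjects who take other vitamin C supplements. In six of the seven dosing weeks a weekly health call is scheduled. In the seventh, Week 27, no health contact is listed, and the only later contact with listed assessments asks about mood, suicidal ideation (through the GDS) and social isolation, not physical health. Equipment return in Weeks 27-28 is by mail or contactless pickup, with no health question listed.

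An event that starts in Week 27 would then reach the record only if the subject volunteered it. What is at stake is complete recording of adverse events, and referral where needed, for the last week of a study-supplied exposure at one site.

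**Working it through.** No sample-size or alpha figure is involved; this is a calendar count.

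**Inputs.** Dosing weeks 1-4 and 25-27 (VI.H.4; notes m and u). Weekly calls through Week 26 (IV.B, VI.J.1). Taper chats in Weeks 25-26 (VI.J.1). Month 6 procedures in Weeks 25-26 (XI.A). Follow-up call in Week 28 (XI.B). Weeks start on a Monday (VI.H).

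**Plan's own figures.** Three weeks starting at Week 25 are Weeks 25, 26 and 27, which agrees with notes m and u. Week 24 + 4 weeks = Week 28, which agrees with a call about one month after the intervention ends.

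**Dosing days.** 4 × 7 + 3 × 7 = 28 + 21 = 49.

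**Uncovered weeks.** Remove the weeks with a weekly call (1-26) from the dosing weeks (1-4, 25-27). Week 27 remains, so 6 of 7 dosing weeks have a weekly call.

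**Uncovered days.** Count Monday of Week 26 as day 1. Week 27 is then days 8-14 and Week 28 is days 15-21. Let *d* be the day of the last contact of any of the three kinds (weekly call, chat or stability screening). Dosing days after it = 14 − *d*.

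| Last contact | *d* | Days after it | Share of 49 |
|---|---|---|---|
| Sunday, Week 26 | 7 | 7 | 14% |
| Friday, Week 26 | 5 | 9 | 18% |
| Tuesday, Week 26 | 2 | 12 | 24% |
| Monday, Week 26 | 1 | 13 | 27% |
| None in Week 26; Sunday, Week 25 | 0 | 14 | 29% |
| None in Week 26; Monday, Week 25 | −6 | 20 | 41% |

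The documents do not fix the weekday of these contacts. If contacts are Monday to Friday only (assumption), the minimum is 9 days. An intervention subject who has both Week 26 chats on different days (assumption) has *d* of at least 2, so at most 12 days. A control subject whose Month 6 calls were finished in Week 25 may have the weekly call as the only Week 26 contact. The last two rows arise only if every Week 26 contact is absent; section VI.H.3 allows a weekly call to be counted as missed.

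**After the fix.** Vitamin C weeks with no listed health enquiry during or after them fall from 1 to 0. The call comes 15 − 14 = 1 to 21 − 14 = 7 days after the last tablet day.

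**Recall period.** Let *w* be the day of the last completed weekly call and *c* the day of the Week 28 call. Recall = *c* − *w*. Shortest: 15 − 7 = 8 days. Longest with a completed Week 26 call: 21 − 1 = 20 days. If the Week 26 call was missed and the Week 25 call was on Monday: 21 − (−6) = 27 days.

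**Dose.** 250 / 2,000 = one-eighth of the daily upper intake level cited in X.A.4.

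**The case against.** The strongest case on the other side has four parts.

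- **The DSMP may settle it.** Sections VI.H.1 and VI.H.3 send adverse-event handling to the DSMP, and section VIII and others defer to the main protocol. Neither is among the documents, and either could require a health question at follow-up. The Schedule of Events has no adverse-event row at any time point, so an empty Week 28 cell is weak evidence. This stands: the point concerns only what this protocol lists, and it rests on the two health-related rows (weekly questionnaire and stability screening) being unmarked at Telephone Follow-Up.
- **The stability screening may already apply.** Section VI.B.1 ties it to every assessment call, and the Week 28 call does administer two assessments. The section heading omits Baseline, which the schedule marks, so it is not a complete list. Against this, neither the heading nor the schedule lists Follow-Up, and the stated purpose is to judge data reliability. The text is unclear; if Week 28 is meant, only the schedule mark is missing.
- **The risk is small.** Section X.A.4 says the effects occur mainly at high doses, and it allows subjects with extra supplementation or a relevant condition to skip the tablet or the pillbox. Week 27 is the seventh week of an unchanged low dose. This stands in full.
- **A Week 28 question is late.** It comes after the last tablet and protects no one during dosing. This also stands; the gain is in recording and referral only.

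Two stronger readings are tempting. A reader might infer that all subjects at all sites have a comparable safety gap of 8 to 20 days before the Week 28 call. The interval exists, but subjects outside OHSU receive no tablet and their chats have ended, so no listed study exposure continues through it. A reader might also infer that the trial collects no adverse events after Week 26. The documents do not show that: the DSMP is not supplied, and staff may record whatever subjects volunteer.

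**Conclusion.** The point holds in a narrow form. As this protocol lists its contacts, OHSU pillbox subjects take study-supplied vitamin C on at least 7 of 49 days (14%) with no physical-health enquiry during or after those days. The range is 7 to 13 days when a Week 26 contact takes place, and larger when none does.

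This assumes that the stability screening does not apply at Week 28 and that neither the DSMP nor the main protocol adds a later enquiry. The documents do not give the number of OHSU subjects; about 40 are anticipated across three sites under this protocol.

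This is a cheap improvement to safety recording at a dose with low expected harm. No endpoint, power or alpha is affected.

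**What to change.** First check the DSMP, and whether the Week 28 call counts as an assessment call under section VI.B.1. If either already provides a health question, only a mark under Telephone Follow-Up in the Schedule of Events is needed.

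Otherwise, for OHSU pillbox subjects in both arms, ask the health items of the I-CONNECT Weekly Questionnaire at the existing Week 28 call, with recall since the last completed weekly call. Mark this under Telephone Follow-Up and handle any events per the DSMP. Extending it to the other sites for uniformity is optional. Dose and chat schedules stay as they are.

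The cost is a few more minutes on a 30-minute call and one schedule mark, with no extra visit or staff. The drawback is retrospective recall longer than the usual week, up to 20 days, or 27 if the Week 26 call was missed and the last was on Monday of Week 25, in a cohort that includes people with MCI.

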Randomization to the control group or intervention group will occur prior to the Baseline visit, but subjects should not be notified of their group assignment until after the Baseline visit to help prevent the subjects from inadvertently unblinding the assessment staff.

If subjects are randomized but then withdraw and do not complete the Baseline visit, they will be removed from the randomization program to ensure study arms remain balanced. These subjects will be classified as drop-outs prior to randomization, as they are not informed of their group assignment.

If cohabitating subjects enroll in the trial, forced randomized will be used to assign the subjects to the

same study condition.

H. Intervention Period

The 24-week intervention period will begin once the Baseline procedures are complete. The intervention period will always start on a Monday.

For all subjects, Week 1 of the intervention period will start no more than two Mondays after the last Baseline-period procedure (the Baseline assessment or the technology installation, as applicable).

If a subject's Week 1 Day 1 is delayed more than 6 months from the date of their Screening visit, the subject will be rescreened. See section VI. E. Eligibility for rescreening details. Screening and Baseline data will be recollected.

1. Video Chat Intervention *Week 1 through Week 24*

The study intervention consists of structured 30-minute video chats between participants and study staff. Video chats will be conducted remotely using an online audio and video communication platform and a video chat device installed in the subject's home. The video chats will be audio and video recorded.

Novel conversation stimuli are provided for each chat, focusing on a theme with three possible topics and corresponding photos, to be visually presented to the participant during the chat via the video chat device. Stimuli include questions targeting three domains of cognition: episodic memory, semantic memory, and executive function. Stimuli will be used to initiate each chat, however subjects may direct the conversation as they find interesting or engaging. Study staff will attempt to maintain a neutral or positive chat tone.

The full chat intervention will last for 24 weeks. Chats will occur four days per week.

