Psychological well-being and person-specific levels of social interaction (i.e., changes in social engagement measured with the I-CONNECT Weekly Questionnaire administered weekly via telephone) will be monitored and controlled in the analyses along with other relevant variables, including APOE 4 status.

Video chats will be recorded and analyzed to determine longitudinal changes in speech patterns.

A. Analyses for Primary Outcomes

MoCA test scores (global cognitive function) are our primary outcome.

Secondary outcomes include: neuropsychological test results in the area of language-based executive function, measured by the T-Cog category fluency test (animals), and memory domains measured by

two T-Cog episodic memory tests (Craft Story Immediate and Delayed Recall). We will allocate a type I error rate of 0.05 for our primary outcome. The results will be cross-validated with NIH Toolbox cognitive batteries as exploratory analyses for those who had NIH Toolbox cognitive assessments. Potential mediation variables include the Psychological Well-Being portion of the NIH Toolbox. If Psychological Well-Being shows significant improvement in the experimental group compared to the control group over 6 months (in univariate analysis using $p < 0.05$), the measurement(s) will be examined as potential mediation factors in statistical models as secondary analyses. The Psychological Well-Being portion of the NIH Toolbox consists of 3 measurements: Positive Affect, Life Satisfaction, and Meaning and Purpose. The questionnaire and references for these scales are detailed in: <http://www.nihtoolbox.org/WhatAndWhy/Emotion/PsychologicalWell-Being/Pages/default.aspx>.

B. Sample Size Estimate

Our previous pilot study (based on a six-week intervention) showed Cohen's $d=0.53$ when comparing pre-post changes in language-based executive functions (Clinical Dementia Rating 0 and 0.5 groups combined) in the control and experimental arms. The sample size ($n=72$ completers for each group) in this trial provides 80% power to detect this difference at $\alpha=0.025$, using a two-tailed test (i.e., total type I error rate= 0.025), based on simulation results using non-pooled standard deviation (SD).

Two separate hypotheses are proposed. Stage I examines the efficacy of the high dose and Stage II examines the efficacy of the maintenance dose. Participants covered under the current protocol will be included into the high dose analysis

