Changes in primary and secondary outcomes between the control and experimental groups will be examined for the efficacy of high dose (month 0 – month 6, Stage I) and maintenance dose (month 6 – month 12, Stage II) using the Mixed-Effect Model Repeated Measure (MMRM) model under ITT. We will conduct per protocol analysis using those who completed at least 80% of targeted conversational sessions (experimental group) and the number of telephone check-ins (control group). The subjects recruited or in trial under the current remote trial protocol will be included where appropriate (i.e., high dose analysis).

Changes in primary and secondary outcomes between the control and experimental groups will be examined for the efficacy of high dose (month 0 – month 6, Stage I) and maintenance dose (month 6 – month 12, Stage II) using the Mixed-Effect Model Repeated Measure (MMRM) model under ITT. We will conduct per protocol analysis using those who completed at least 80% of targeted conversational sessions (experimental group) and the number of telephone check-ins (control group).

Changes in primary and secondary outcomes between the control and experimental groups will be examined for the efficacy of high dose (month 0 – month 6, Stage I) and maintenance dose (month 6 – month 12, Stage II) using the Mixed-Effect Model Repeated Measure (MMRM) model under ITT. We will conduct per protocol analysis using those who completed at least 80% of targeted conversational sessions (experimental group) and the number of telephone check-ins (control group).

[figure not shown]

Figure 1. Trial Dose Stages: Sample size for one group (MCI or normal cognition; both groups have the same planned sample size)

Changes in primary and secondary outcomes between the control and experimental groups will be examined for the efficacy of the high dose (Baseline-Month 6, Stage I) and the maintenance dose (Month 6-Month 12, Stage II) using the Mixed-Effect Model Repeated Measure (MMRM) model under intention-to-treat (ITT). We will conduct per-protocol analysis using those who completed at least 80% of the targeted conversational sessions (experimental group) and telephone check-ins (control group).

C. Analyses proposed for the New Aim 4

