Subject Compensation		X ^{b,s}	X				X ^c		
NEO-FFI and NIH Toolbox Emotional Domain Questionnaires ^d			X				X		
Clinician Diagnosis ^o		X					X		
Trial Eligibility Assessment ^f	X	X							
Post-Study Resources		X ^e					X		X
Randomization			X ^g						
Family History of Dementia			X						
Physical Evaluation (Form B1)			X						
Saliva Collection for APOE4			X ^l						
Vitamin C Pillbox ⁱ				X	X ^u		X ^u	X	
Video Chat Device ^j				X				X	
PANAS ^{h,j}					X	X			
Video Chat Intervention ^j					X	X			
I-CONNECT Weekly Questionnaire ^k					X	X			
Vitamin C Medication Adherence ⁱ					X ^m	X ^m			
Qualitative Evaluation (Subject) ^j					X ⁿ				

- a) Subjects may choose to provide emergency contact and primary care provider contact information; this is optional.
- b) Compensation will be provided to all subjects who consent to participate, including screen failures.
- c) Compensation to be provided once all procedures are completed.
- d) Questionnaires will be provided for subjects to complete independently. If the subject does not successfully complete the questionnaires on his or her own, the questionnaires will be completed with staff assistance.
- e) Resources to be provided at this time point only if subject is a screen failure.
- f) Final eligibility assessment to be completed upon clinician diagnosis.
- g) Randomization to intervention/control occurs once eligibility is determined, prior to the Baseline visit. Subjects should not be notified of group assignment until after Baseline to prevent them from unblinding the assessment staff.
- h) The PANAS will be administered at the beginning and the end of the subject's first video chat session each week.
- i) OHSU subjects only.
- j) Intervention group only. Control group does not receive.
- k) Administered weekly via telephone.
- l) This procedure is optional for subjects. If sample cannot be obtained, collection will be re-attempted at a future time point.
- m) Occurs daily in weeks 1-4 and 25-27. If the subject misses the target time but remembers the same day, the subject should take the vitamin as soon as they remember. If the subject does not remember until the next day or later, the subject should skip the missed dose and leave the vitamin in the pillbox.
- n) To be completed at the conclusion of the Week 24 video chats. Administration and responses will be audio and video recorded.

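### Section VIII says changes in weekly social engagement, recorded only after randomisation, will be controlled in unnamed analyses, and does not exempt the ITT efficacy models

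*Combined protocol and SAP*

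**What the plan says.** The general text of section VIII, before heading A, states that "changes in social engagement measured with the I-CONNECT Weekly Questionnaire administered weekly via telephone) will be monitored and controlled in the analyses". The same sentence lists psychological well-being and APOE4 status as variables to be controlled. It does not say which analyses it covers.

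Section VI.H.3 describes the instrument: "Health and social activities will be monitored with a brief survey, the I-CONNECT Weekly Questionnaire". Its stated timing is "Weekly During Intervention Period & Dose Tapering". In the Schedule of Events (section XI.B), the row "I-CONNECT Weekly Questionnaire ^k" is marked only under Intervention Period and Dose Tapering.

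On the order of events, section VI.G says "Randomization to the control group or intervention group will occur prior to the Baseline visit", and section VI.H says "The 24-week intervention period will begin once the Baseline procedures are complete".

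The efficacy analysis, set out under section VIII.B, compares arms on change in the primary and secondary outcomes "using the Mixed-Effect Model Repeated Measure (MMRM) model under intention-to-treat (ITT"). No covariates are listed there, and nothing says that the preamble does not apply. Section VIII opens by deferring to the main I-CONNECT protocol for the analysis approach.

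**The concern.** An ITT comparison is meant to estimate the total effect of being assigned to the chats. Section II gives more social interaction as the route by which the intervention should help cognition. A measure of social engagement taken during treatment may therefore be affected by assignment. Conditioning on such a variable can remove part of the effect that the trial is trying to measure. If engagement and cognition also share unmeasured causes, it can create an arm difference where there is none.

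The sentence places engagement beside APOE4 status, an ordinary adjustment variable, so covariate adjustment is its natural reading. It also stands ahead of the heading for the primary-outcome analyses. An analyst could reasonably apply it to the models that decide whether the trial succeeded.

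**Working it through.** **Step 1. Timing.** The order is screening, clinician diagnosis, randomisation, Baseline visit, Week 1 (sections VI.F to VI.H and XI). The Weekly Questionnaire starts in Week 1 and has no screening or Baseline administration. Every value, and so every change, is post-randomisation.

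**Step 2. The other variables in the sentence.** APOE4 is a fixed genotype, so its date of collection does not matter. Psychological well-being is measured at Baseline and Month 6, and the sentence does not say which value is meant. The Baseline value comes after randomisation, but section VI.G says that "subjects should not be notified of their group assignment until after the Baseline visit", so adjusting for it is harmless. Month 6 or change in well-being raises the same problem as engagement, but section VIII.A already treats improvement in well-being as a possible mediator in secondary analyses. Engagement is given no such limit.

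**Step 3. The plan's own power figure.** Inputs from section VIII.B: 72 completers per group, d = 0.53, two-sided alpha 0.025, stated power 80%. With SD 1, SE = sqrt(2/72) = 0.1667 and the noncentrality is 0.53/0.1667 = 3.18. The noncentral t with 142 df gives 81.9% (normal approximation 82.6%). This agrees with 80% closely enough, given that the plan used simulation with non-pooled SD. At two-sided 0.05, the level that section VIII.A gives for the primary outcome, power is 88.5%.

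**Step 4. What adjustment could do (illustration).** Take a linear model of outcome on arm plus one post-randomisation covariate, each with within-arm SD 1. Let rho be the within-arm correlation of covariate and outcome, and dM the arm difference in the covariate in SD. Neither is in the documents; both are assumed.

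- Expected arm coefficient = d - rho × dM
- SE = sqrt((1 - rho²) × (2/72) × (1 + dM²/4))
- Power from the noncentral t with 141 df

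Example with rho = 0.3, dM = 0.5: estimate = 0.53 - 0.15 = 0.38; SE = sqrt(0.91 × 0.02778 × 1.0625) = 0.1639; noncentrality = 2.32.

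| rho | dM | Estimate | SE | Power at 0.025 | Power at 0.05 |
|---|---|---|---|---|---|
| unadjusted | - | 0.53 | 0.1667 | 82% | 88% |
| 0.1 | 0.25 | 0.505 | 0.1671 | 77% | 85% |
| 0.3 | 0.5 | 0.38 | 0.1639 | 52% | 63% |
| 0.3 | 1.0 | 0.23 | 0.1778 | 17% | 25% |
| -0.3 | 0.5 | 0.68 | 0.1639 | 97% | 98% |

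Now set the true total effect to zero, with two-sided alpha 0.025 (nominal 1.25% per tail). At rho 0.3, dM 0.5 the adjusted test favours control 9.1% of the time. At rho -0.3, dM 0.5 it falsely favours the intervention 9.1% of the time. If rho or dM is zero, the shift rho × dM is zero.

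**Limits of Step 4.** The value 0.53 is a pilot effect on language-based executive function, not MoCA. The primary MoCA analysis uses only the pre-pandemic cohort (section II, Aim 1), so its n may be below 72 per arm. One covariate stands in for a weekly series in a repeated-measures model. The table shows that bias is possible in both directions; it does not predict its size.

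**The case against.** The best reply is that the efficacy text is specific and the preamble is general. Section VIII.B names an ITT mixed model and no covariate; if the specific text governs, engagement is not in that model. The handling of well-being supports this: the preamble lists it as controlled, yet section VIII.A assigns it to secondary mediation analyses, so being controlled need not mean being a covariate in the primary model. Moreover, this document is a remote-conduct supplement for about 40 subjects, and the primary MoCA analysis rests on the pre-pandemic cohort, so the covariate list most naturally belongs in the main protocol.

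This stands in part. A reader might infer that the primary analysis will adjust for weekly engagement. The documents do not support that: they leave it open, and the main protocol may close it. The reply does not remove the sentence, which states a rule in this document's own words and carries no limit for engagement. If the main protocol excludes engagement, the two texts must be reconciled; if it does not, the problem is live.

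A second reply is that the covariate is loosely defined. There is no scoring, no reference week and no statement whether study chats count. If only contact outside the study counts, or if change is taken from Week 1 when chats have already begun, the arms may differ little. This also stands. A reader might infer that engagement is certainly a consequence of assignment, or that adjustment would certainly mask a benefit. The documents support only that it may be affected by assignment, and give neither the size nor the sign of any bias.

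**Conclusion.** The sentence is wrong as written, because it permits, without limit, control for a variable that exists only after randomisation and may lie on the causal path. If it is followed in the primary or secondary ITT models, the arm coefficient need not estimate the total effect of assignment. The conclusion rests on the timing in sections VI.G, VI.H and XI.B, the hypothesis in section II, and the absence of any exemption in section VIII; it does not depend on the illustrative figures.

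The size of any bias cannot be derived from the documents. It requires both an arm difference in measured engagement and a within-arm relation between engagement and outcome. Confidence is medium, because the main protocol's covariate list was not available. The criticism does not extend to APOE4 status or to Baseline well-being.

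**What to change.** Amend the preamble sentence in section VIII to say two things:

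- The primary and secondary ITT mixed models adjust only for variables that are fixed or measured before the intervention starts, for example the baseline value of the outcome, the randomisation balancing factors and APOE4 status.
- Weekly social engagement, and Month 6 or change in psychological well-being, are used only in labelled secondary mediation or exploratory analyses.

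Then reconcile this wording with the covariate list in the main I-CONNECT protocol, so that the two documents give one rule. The cost is a change of SAP wording; no new data are needed, and the stated power basis is unaffected.
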